
The protocol has been amended following the comments received from the Center for Biologics Evaluation and Research. The following changes were implemented:
 
• Objectives: The protocol has been modified to include pregnancies irrespective of low or high-risk status (to reflect the current use of the vaccine). A primary objective has been added to rule out a two-fold increase in the incidence of four pre-specified maternal and infant adverse events. A secondary objective has been added to explore differences in eight other pre-specified maternal and infant adverse events.• Endpoints:
– The list of endpoints has been reviewed in view of their medical and scientific significance. Prioritization of endpoints was also based on the 2014 collaboration between the Brighton Collaboration Foundation and the World Health Organization (WHO) to address gaps in the safety assessment of vaccines during pregnancy (1). The following endpoints were removed: Gestational diabetes, premature uterine contractions, macrosomia, fetal distress, placenta previa, and delivery methods. The following endpoints were added: Small for gestational age (SGA), preterm delivery, neonatal death, maternal death, and preterm pre-labor rupture of membranes (PPROM).– Spontaneous abortion with or without congenital anomaly (CA) and therapeutic abortion with or without CA occur, by definition, before 20 weeks of gestation (2). Therefore, these events will not be part of the main analysis on the safety of Boostrix administered after the 27th week of gestation. However, the incidence of these events will be collected for subjects who received Boostrix prior to the 27th week of gestation and described in the study report.– Endpoints have been classified as either primary or secondary.• Risk factors: additional factors defining a pregnancy as “high-risk” have been added.• Case definitions: Pre-specified maternal and infant adverse events reflect the data captured by ICD-9 and ICD-10 coding according to the clinical practice of obstetrics.• Further details on the statistical methods have been added for each endpoint.	

Protocol Amendment 2 Rationale

Amendment number: Amendment 2

Rationale/background for changes:

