Intra-uterine infections such as chorioamnionitis and endometritis	All pregnant women eligible for inclusion/exclusion criteria	Adjusted Poisson regression model accounting for follow up time, with robust variance estimate
Small for gestational age (SGA)	KPSC live born infant, singleton only**	Adjusted Poisson regression model, with robust variance estimate
Preterm delivery	Pregnant women with live birth, with index (vaccination) date prior to 37 weeks gestation	Adjusted Poisson regression model, with robust variance estimate
Secondary endpoints	Analytic population	Statistical Methods
Transfusion during delivery hospitalization	Pregnant women with delivery hospitalization	Adjusted Poisson regression model
Poor fetal growth	All pregnant women eligible for inclusion/exclusion criteria	Adjusted Poisson regression model accounting for follow up time, with robust variance estimate
Stillbirth/fetal death*	Pregnant women with pregnancy outcome	Adjusted Poisson regression model
Neonatal death (within 28 days of birth)	KPSC live born infants	Adjusted Poisson regression model
Maternal death (while pregnant or within 42 days of end of pregnancy)	All pregnant women eligible for inclusion/exclusion criteria	Adjusted Poisson regression model accounting for follow up time
Placental abruption	All pregnant women eligible for inclusion/exclusion criteria	Adjusted Poisson regression model accounting for follow up time
Preterm pre-labor rupture of membranes (PPROM)	All pregnant women, with index (vaccination) date prior to 37 weeks gestation	Adjusted Poisson regression model accounting for follow up time
Congenital anomalies (CA) at birth and through 6 months of age	KPSC live born infants	Adjusted Poisson regression model, with robust variance estimate if outcome is common
Spontaneous abortion	Pregnant women exposed to Boostrix before the 27th week of gestation	Descriptive analysis (proportion)
Therapeutic abortion	Pregnant women exposed to Boostrix before the 27th week of gestation	Descriptive analysis (proportion)

* Stillbirth/fetal death will be described with or without congenital anomalies separately, but will be analyzed as one outcome.

** There are no well accepted SGA metrics for infants born to pregnant women with multiple gestation.

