The algorithms for identification of primary and secondary endpoints are described in the DMP. Except SGA, preterm delivery, and transfusion during delivery hospitalization, AEs identified through the algorithms will be chart reviewed to confirm the diagnosis and the onset (when applicable). Analyses of endpoints will be based on confirmed cases. For AEs with a chart-reviewed onset date, the event start date will be the onset date; for AEs without a chart-reviewed onset date (unknown or inapplicable), the event start date will be the earliest confirmed diagnosis date. To be a confirmed case, the event start date needs to be after the index date. Some AEs might be diagnosed during the delivery hospitalization, and have an event start date after the delivery date. For pre-eclampsia and/or eclampsia, intra-uterine infections, and poor fetal growth, the event date needs to be on or before the delivery date. For placental abruption and PPROM, if the event start date is after the delivery date, the delivery date will be used as the event start date.

SGA will be defined based on reference values derived by Talge et al. with a cut-off of <10th percentile (1). Talge et al used 2009-2010 US natality data and corrected for likely errors in gestational age dating to yield an up-to-date birth weight for gestational age reference. The

evaluation of SGA is limited to singleton births because the reference values for SGA definition are established based on singleton births.

Stillbirth/fetal death has a number of different and legally mandated definitions (2). This study will use ACOG's definition which defines stillbirth/fetal deaths at 20 completed weeks gestation or greater (if the gestational age is known). Maternal death will include all non-accidental deaths while pregnant or within 42 days of end of pregnancy. Neonatal death will include deaths within 28 days of birth among KPSC live born infants.

For a multiple gestation pregnancy, the pregnancy outcome will be recorded for each fetus, while the endpoint will be defined by the worst scenario. For examples, the woman will be considered to have a pre-term delivery, if any fetus was delivered pre-term after the index date. The woman will also be considered to have spontaneous abortion, therapeutic abortion, or stillbirth/fetal death if any fetus experienced these pregnancy outcomes after the index date.

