## Appendix A: Table Shells

Table 6: Study population and subgroups for descriptive analysis

	Exposed
Pregnant women eligible per inclusion/exclusion criteria, n	
With pregnancy outcome, n (%)	
With unknown pregnancy outcome, n (%)	
Lost to follow up, n (%)	
Pregnant women with multiple gestation, n (%)	
Pregnant women with delivery hospitalization, n (%)	
Pregnant women with index date prior to 37 weeks gestation, n (%)	
With live birth, n (%)	
KPSC live born infants, n	
Singleton only, n (%)	

Table 7. Baseline characteristicsa of pregnant women vaccinated with Boostrix before the 27th week of gestation

	Exposed N =
Maternal age at pregnancy start, years	
mean (sd)	
median	
Q1, Q3	
range	
Race/ethnicity, n (%)	
White	
Black	
Hispanic	
Asian	
Other	
Gestational age in weeks at index date, n (%)	
27-30	
31-36	
≥37	
Current smoker, n (%)	
Yes	
No	
Alcohol use, n (%)	
Yes	
No	
Continuous membership, n (%)	
Yes	
No	
Medicaid insurance, n (%)	
Yes	
No	
Any hospitalization or ED visit, n (%)	
Yes	
No	
Number of outpatient visits, n (%)	
0-4	
5-12	
≥13	
Number of previous pregnancies, n (%)	
0	
1	
≥2	
Missing	
History of pregnancy loss, n (%)	
Yes	
No	
Season of pregnancy start, n (%)	
September-March	
April-August	
Received other vaccines b , n (%)	
Yes	
No	
Received vaccines containing diphtheria, tetanus toxoid, or pertussis antigens within one year before pregnancy, n (%)	
Yes	
No	
High-risk medical condition, n (%)	
Multiple gestation	
Thyroiditis	
Diabetes	
Other autoimmune diseases	
Renal diseases	
Cardiac diseases	
Pre-pregnancy obesity c	
Missing	
Pre-existing hypertension	
Rhesus sensitization	
HIV infection	
Syphilis infection	
Cervical incompetence	

a Baseline characteristics were defined from pregnancy start to index (vaccination) date, unless otherwise specifiedb Other vaccines included: inactivated influenza vaccine (xx%), hepatitis A/hepatitis B vaccine (xx%), human papillomavirus vaccine (xx%), and other (xx%).c BMI>40 within 6 months prior to pregnancy start

Table 8. Characteristics of KPSC live born infants with mothers vaccinated with Boostrix before the 27th week of gestation

	Exposed
	N =
Sex, n (%)	
F	
M	
Gestational age in weeks at birth, n (%)	
27-33	
34-36	
37-39	
≥40	
Birth weight, g	
mean (sd)	
median	
Q1, Q3	
range	
Missing	
Birth length, cm	
mean (sd)	
median	
Q1, Q3	
range	
Missing	
Head circumference, cm	
mean (sd)	
median	
Q1, Q3	
range	
Missing	

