a Identified among all pregnant women eligible for descriptive analysisb Identified among KPSC live born infants, singleton onlyc Identified among pregnant women with live birth, with index (vaccination) date prior to 37 weeks gestationd Identified among pregnant women with index (vaccination) date prior to 37 weeks gestatione Identified among pregnant women with pregnancy outcomef Identified among pregnant women with delivery hospitalizationg Identified among KPSC live born infantsh Wilson score interval with continuity correction

\* N/A=Not Applicable

Table 10. Summary of signaled events

	Exposed			Unexposed				
	Number of events	Number of Persons (or person years)	Incidence per 1000 persons or person-years (95% CI)		Number of events	Number of Persons (or person years)	Incidence per 1000 persons or person-years (95% CI)	
Number of confirmed events		N/A	N/A			N/A	N/A	
Number of potential cases identified by the algorithm		N/A	N/A			N/A	N/A	
Confirmation rate		N/A	N/A			N/A	N/A	
Age at pregnancy start, years								
<18								
18-24								
25-34								
≥35								
Received other vaccines during pregnancy, n (%)								
Yes								
No								
High-risk medical condition, n (%)								
Thyroiditis								
Yes								
No								
Diabetes								
Yes								
No								
...								
Gestational age at event date								
27th week		N/A	N/A			N/A	N/A	
28th week		N/A	N/A			N/A	N/A	
29th week		N/A	N/A			N/A	N/A	
...		N/A	N/A			N/A	N/A	
ICD diagnosis code and description								
...		N/A	N/A			N/A	N/A	
...		N/A	N/A			N/A	N/A	
...		N/A	N/A			N/A	N/A	
...		N/A	N/A			N/A	N/A	
...		N/A	N/A			N/A	N/A	

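### In women vaccinated before week 27, the abortion denominators include those vaccinated at 20-26 weeks, who cannot have the event, and Shell 7 cannot show when they were vaccinated

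*Protocol*

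**What the plan says.** Secondary objective 2 is a descriptive, single-arm account of events in women vaccinated before week 27. It is the only place where abortion is reported.

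- **Denominator.** Protocol Table 7 (section 6.2.2) gives the population for both abortion endpoints as "Pregnant women exposed to Boostrix before the 27th week of gestation", summarised as a proportion. In SAP Appendix A, Shell 9, footnote e to the abortion rows reads "Identified among pregnant women with pregnancy outcome". Neither sets an upper limit of 20 weeks on the index date.
- **Event definition.** The protocol's rationale for the amendment before Amendment 2 (Endpoints) says that spontaneous and therapeutic abortion "occur, by definition, before 20 weeks of gestation". SAP 3.2.3 adopts a definition that "defines stillbirth/fetal deaths at 20 completed weeks gestation or greater". It classes a woman with a multiple pregnancy as having an abortion "if any fetus experienced these pregnancy outcomes after the index date".
- **Treatment of other endpoints.** SAP 3.2.1 removes women indexed at 37 weeks or later from preterm delivery and PPROM, because they can no longer have the event. Its list has no entry for abortion.
- **Timing.** Shell 7, the baseline table for this group, has a block headed "Gestational age in weeks at index date, n" with rows 27-30, 31-36 and ≥37 weeks. These are the Shell 2 rows for the main cohort.

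**The concern.** A proportion is diluted when its denominator holds people who cannot be cases, and the error here always runs toward reassurance. The same applies to the upper confidence limit, which is the informative figure if no abortions are seen.

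A reader of the report could not detect or correct this. Every Shell 7 index-date row would be empty, and no other planned report table gives vaccination timing for the group. The uptake reports in protocol section 8.3 split only at 27 weeks.

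**Working it through.** **1. Can a woman vaccinated at 20-26 weeks be a case?** The event must occur before 20 weeks (amendment rationale) and after the index date (SAP 3.2.3). With an index date at 20 weeks or later, no date meets both conditions. For fetal loss, the SAP's stillbirth definition agrees, since it takes over at 20 completed weeks. For therapeutic abortion, the amendment rationale is the only explicit source of the limit.

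**2. Size of the group.** Protocol Table 4 (2016 feasibility data) gives 250 of 19,804 women vaccinated before 27 weeks: 250/19,804 = 1.26%, stated as 1.3%. The other 19,554 are 98.7%, as stated. Scaled to the planned 15,000 women vaccinated from week 27: 250 × 15,000/19,554 = 191.8, about 192 women. This assumes that the 2016 pattern holds and that the eligibility criteria leave the ratio unchanged.

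**3. Dilution.** Take N women in the denominator, x events, and a share f vaccinated at 20-26 weeks.

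- Reported proportion = x/N
- At-risk proportion = x/[N(1-f)]
- Reported = (1-f) × at-risk; at-risk/reported = 1/(1-f)

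**4. Numbers.** The documents do not give f, so the values below are assumptions. Intervals are the 95% Wilson score interval with continuity correction, as planned in SAP 4.4. The event counts of 0 and 2 are illustrative.

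| Assumed f | Women in denominator | At-risk ÷ reported | 0 events: upper limit | 2 events: proportion (95% CI) |
|---|---|---|---|---|
| As planned (all) | 192 | – | 2.44% | 1.04% (0.18-4.11) |
| 25% | 144 | 1.33 | 3.24% | 1.39% (0.24-5.44) |
| 50% | 96 | 2.00 | 4.79% | 2.08% (0.36-8.04) |
| 75% | 48 | 4.00 | 9.23% | 4.17% (0.72-15.43) |
| 90% | 19 | about 10 | 20.92% | 10.53% (1.84-34.54) |

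**5. Shell 7.** The group is defined by an index date before week 27, and the lowest row starts at 27. No woman in the group fits any row.

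**6. Shell 8.** Its rows are gestational age at birth: 27-33, 34-36, 37-39 and ≥40 weeks. Infants of early-vaccinated mothers can fall in each of them. Only a row below 27 weeks is missing.

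**The case against.** - **The denominator matches the stated objective.** Objective 2 is to describe incidence in women vaccinated before week 27. The amendment rationale states the 20-week limit and then says that abortions will be described in exactly that group. This stands as far as labelling goes: the planned figure is a correct proportion of its named population. It is still a poor measure of abortion risk after vaccination, and it departs from the rule that the SAP applies to preterm delivery and PPROM.
- **SAP 4.4 may already restrict.** It takes as denominator the women in whom the condition is assessable, which could be read as excluding those past 20 weeks. But it does not define assessable as at risk, and Shell 9 footnote e ties these rows to having a pregnancy outcome.
- **The limit is less firm for therapeutic abortion.** This stands. The SAP's stillbirth definition does not bound it, and the event algorithms are in the Data Management Plan, which is not among these documents. If another limit is intended, it should be stated.
- **A cut at 20 weeks is only a partial remedy.** A woman vaccinated at 19 weeks has about one week at risk, yet counts the same as one vaccinated at 6 weeks. True, and a further reason to show vaccination timing.
- **Little depends on it.** The analysis is single-arm with no hypothesis test, SAP 4.4 expects a very small sample, and protocol section 7 expects abortions to be rare. This stands and limits the importance of the point.

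A reader might also infer that Shell 8 cannot be filled, or that births before 27 weeks go unreported. Neither follows. Shell 8 describes age at birth, not at vaccination. Shell 9 counts live births before 27 weeks under preterm delivery, because footnote c takes all women with a live birth and an index date before 37 weeks.

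**Conclusion.** The point holds as a minor correction. Under the documents' own definitions, the abortion denominators include women who cannot be cases, so the reported proportion is (1-f) times the at-risk proportion. Shell 7, as drawn, cannot show vaccination timing for this group.

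The direction of the error is certain once the 20-week limit is accepted. Its size is not: the factor of 1.33 to about 10 rests on an assumed f of 25% to 90%, and the figure of about 192 women rests on the 2016 pattern. It would be tempting to quote a specific understated abortion risk, but the documents give neither an abortion rate nor the share vaccinated at 20-26 weeks, so they support none.

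Nor does the point reach the safety conclusions. The four primary endpoints and the comparative secondary analyses use women vaccinated from week 27 and their matched controls, and are unaffected.

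**What to change.** 1. In protocol Table 7, SAP 3.2.1 and Shell 9, restrict the denominator for spontaneous and therapeutic abortion to women with an index date before 20 weeks 0 days. Alternatively, keep the full group and report <20 and 20-26 weeks separately.
2. State the 20-week limit for therapeutic abortion in the SAP, or state whichever limit is intended.
3. Replace the Shell 7 index-date rows with categories below 27 weeks that include a cut at 20 weeks.
4. As a minor addition, put a <27-week row in Shell 8.

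The cost is wording and shell edits. No new data are needed, since the study already derives gestational age at the index date for every woman.

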6.2.3. Analyses interpretation

Analysis of primary endpoints will be used to evaluate the safety of maternal vaccination and concluded to be non-inferior if the upper limit of the 98.75% CI for the adjusted relative risk is below 2.

While the analysis of primary endpoints will be used to evaluate the safety of maternal vaccination with sufficient statistical power, the analysis of secondary endpoints will be used for hypothesis generation/signal detection.

6.3. Sample size considerations

The power computation for the primary objective was performed using PASS non-inferiority of two independent proportions using Miettinen and Nurminen method. Although the power is not based on the Poisson regression model, it is expected to reflect the power on the planned analysis since inference on proportion and incidence rate provide similar results when incidence rates are low.

The following table (Table 8) shows the power to rule out a two-fold increase considering an assumed possible design bias leading to a 1.25 relative risk increase.

To be able to make independent conclusions for each of the four primary endpoints while controlling the type I error below 2.5%, a Bonferroni adjustment will be used, i.e., each primary endpoint will be evaluated using a one-sided 0.625% (2.5% type I error / 4 primary endpoints) nominal type I error. More specifically, the upper limit of the two-sided 98.75% CI will be used to make conclusions.

Considering that the four primary endpoints are expected to have an incidence rate above 1%, the power to conclude that maternal immunization is non-inferior for any primary endpoint is at least 95% and the power to conclude that maternal immunization is non-inferior for all 4 primary endpoints is at least 80% (100% - 4*beta).

Table 8 Power to rule out a two-fold increase with 15,000 pregnant women in each cohort

Incidence rate in unvaccinated cohort	One-sided type I nominal error	True relative risk	Power	Beta
1%	0.625%	1.25	95.7%	4.3%

7. STUDY CONSIDERATIONS

Most of the Boostrix exposures during pregnancy will occur at 27 weeks gestation or later. As such, we expect pregnancy outcomes that occur earlier in pregnancy such as spontaneous abortion and therapeutic abortion to be rare in our study. Furthermore, while we will describe the frequency of congenital anomalies among the exposed and unexposed cohorts, we note that the most plausible time period for development of congenital anomalies is during early pregnancy (35). Cautious interpretation of maternal Boostrix immunization and congenital anomalies is warranted.

One potential limitation is that the exposed (Boostrix vaccinated) cohort and the unexposed cohort come from different time periods. With the exposed cohort from the ICD-10 era and the unexposed cohort from the ICD-9 era there is a potential risk of bias if the prevalence of adverse events is higher or lower in either exposed or unexposed cohorts due to coding variation or secular trends. This issue is not specific to KPSC but rather affects all health care organizations and similar research conducted in the U.S. However, this is not a major concern at KPSC as there is specific mapping (crosswalk) between ICD-9 and ICD-10 for all of the outcomes (36, 37). Most importantly, no matter which system is used, a comprehensive list of codes will be used to identify all potential events of interest. In addition, a review of medical records will be conducted to determine whether the events are truly incident events with onset after the index date (vaccination date for the exposed). Similarly, by using a historical cohort to identify the unexposed group to compare to a current exposed cohort, there is a concern that the baseline incidence of the selected safety endpoints will vary significantly between the Tdap (*Boostrix*) vaccination period and the historical comparison period. However, the advantage of comparing to a historical population of pregnant women during approximately 2012-2013 is that we are identifying an unvaccinated group during a period when prenatal Tdap vaccine uptake was low, making these pregnant women more representative of an unvaccinated cohort. A current unvaccinated cohort would yield a small and selective sample (given over 70% Tdap uptake) that is not representative of an unvaccinated group and would be affected by confounding by indication.

If a safety signal is identified, further exploration of the data will be completed to investigate alternative potential sources for the Boostrix-outcome association, including but not limited to changing secular trends or coding practices.

8. CONDUCT OF THE STUDY

GlaxoSmithKline (GSK) will engage KPSC to provide activities including conducting the study on behalf of GSK. The study will be conducted by the Investigator at KPSC's premises under the oversight of the sponsor, GSK. Through this partnership, we will provide critical information about the safety of maternal vaccination with Boostrix in a community setting.

8.1. Regulatory and ethical considerations

The study will be conducted in accordance with all applicable regulatory requirements, including all applicable subject privacy requirements and the guiding principles of the Declaration of Helsinki, International Ethical Guidelines for Epidemiological Studies (CIOMS), FDA Best Practices for Conducting and Reporting Pharmacoepidemiologic Safety Studies using Electronic Healthcare Data, and ISPE guidelines for Good Pharmacovigilance Practice (GPP).

The KPSC team will obtain approval of the final protocol from the Institutional Review Board (IRB) at KPSC prior to study start.

